# 4.8.3 Screening assessments

For those who remain interested following discussions about the and appear to meet eligibility criteria, the consent form will be signed and the screening visit will be conducted. This visit will include completion of assessments to confirm inclusion and exclusion criteria. The Nurse Practitioner will complete a medical history, a physical exam, a rapid blood test for HIV, a pregnancy test for women, and collect 10ml of blood for liver function tests. Research staff will complete baseline assessments described in section 3.7 of this protocol. Those who are not eligible will receive a listing of treatment providers and encouraged to make contact for help with their substance use problems. For those who appear eligible following the screening visit, an appointment for initiating the intervention will be scheduled within 1 or 2 days.

Scale (COWS; Wesson & Ling, 2003), an 11-item scale designed to be administered by a clinician and that can be used in both inpatient and outpatient settings to reproducibly rate common signs and symptoms of opiate withdrawal and monitor these symptoms over time. The summed score for the complete scale will be used to determine the stage of opiate withdrawal and assess the level of physical dependence on opioids. Under the supervision of the NP, COWS will be used as an objective measure of withdrawal and buprenorphine/naloxone treatment will not initiate until the COWS score falls within the 8 -12 range. If the score is below 8, participants will be asked to the COWS will be re-administered in one hour and patients will receive a careful explanation of why medications cannot be started until clear withdrawal symptoms are present. When withdrawal symptoms are sufficient to initiate medication, patients will be given a 4 mg dose. In this trial, we will use generic buprenorphine/naloxone tablets or film that are easily administered by placing the tablets or film under the tongue and waiting for them to dissolve. The COWS will be repeated in one to three hours to assess the reduction in symptoms. It is expected based upon extensive clinical practice that participants will receive relief from opiate withdrawal symptoms with 4-8 mg doses of buprenorphine/naloxone on day 1 (e.g. a total day 1 dose of 8 mg). However, additional dose(s) may be given to those participants in whom withdrawal symptoms remain after receiving 8 mg of medication. In such cases, the Nurse Practitioner will increase the dosage but no more than 16 mg of buprenorphine/naloxone will be given to a participant on day 1 of induction. As with any pharmacotherapy, the goal of buprenorphine/naloxone treatment is to use the minimum effective dose. The immediate goal of buprenorphine/naloxone therapy is to alleviate withdrawal symptoms, with longer-term goals of reducing drug craving, and reducing or eliminating use of opioids. If patients have problems adjusting to buprenorphine/naloxone (e.g., experience persistent withdrawal symptoms or continue to feel compelled to use illicit drugs), the dose may need to be increased. After stabilization, a three-day supply will be provided to the participant with simple instructions for self-administration.

For those who fail to reach threshold for beginning induction while the mobile team is present and the participant in judged by the Nurse Practitioner to be appropriate for self-induction instructions for medication administration will be provided. This "self-induction" procedure has now become quite common (Lee, Vocci, & Fiellin, 2014).

Participants will be asked to maintain contact with the NP on the morning of the following day to assess symptoms of withdrawal. If the participant is not in withdrawal on the morning of day 2, the day 1 dosage will be maintained. If the participant reports feelings of lethargy or sedation, on the next morning the day 2 dosage will be reduced.by 2mgs. If the participant reports feelings of withdrawal on the morning of the second, day the day 2 dosage will be increase by 4mgs.

The final day of dose adjustment will typically be day 3. On the morning of day 3, the participant will be assessed by the NP for signs of sedation or withdrawal and adjust dosages accordingly. Once the stable dose has been determined, the participant will be given a one-week supply of medication and scheduled for an appointment the following week for assessment by the NP and receipt of the second week of medication. This procedure will be continued for the remainder of the treatment month. Participants will meet with the NP weekly, and be invited to have telephone contact as needed.

MAT engagement during the month of intervention will be facilitated by the Peer Recovery Specialist (PRS). The purpose of a PRS is to support the participant in their recovery process. In addition, the project will provide intensive training and ongoing consultation on MAT. The PRS hired for this study will also receive intensive training focused on addiction as a chronic medical condition, motivational enhancement strategies and facilitating short-term behavioral contracts. The PRS will meet with the participant a minimum of 3 times per week and be available for telephone counseling and support throughout the one-month intervention period.

The mobile team's Case Management (CM) function will be performed by a master's level social worker. The CM will have primary responsibility for identifying the treatment program that best meets the needs of the participant. The CM effort will be sharply focused on identifying and removing barriers to MAT treatment engagement. This will include completing medication authorization forms and insurance enrollment if necessary, and then making referrals to additional supports, including mental health treatment, housing, medical, legal support, and peer-based recovery supports in the community. The CM will work collaboratively with participants to remove barriers to care and to enhance program outcomes and to provide psychosocial support.

The mobile team will insure that there is a clear plan for rapid engagement with ongoing treatment as soon as possible. Buprenorphine/naloxone will be provided during the time of transition to their long-term provider for up to 1 month. Telephone support will be available should participants have questions or need assistance and the mobile team will also have daily contact with participants until they complete contact with their ongoing provider.

## Comparison group – Treatment as usual

During the same period of time, participants will also be recruited at the City of Philadelphia Behavioral Health System Behavioral Assessment Centers (BAC) and Crisis Response Centers (CRC) located at Episcopal Hospital serving Kensington area and Hall Mercer BAC/CRC (a University of Pennsylvania program) serving South Philadelphia area. Two research assistants from the TRI-PHMC will enroll and follow-up 125 participants at BAC/CRC. The participants will complete the same assessments at baseline, 1- and 6-month follow-up. Authorization for the Philadelphia Department of Public Health to look shared information about their subsequent use of health department services (CARES database, http://www.phila.gov/hhs/data/Pages/Cares.aspx) will also be requested in the consent form. Research staff will only conduct assessments. Treatment engagement services will be provided by the staff of the BAC/CRC as usual.

## 4.10 Subject Withdrawal

Participants may choose to withdraw from the study at any time. They do this by providing verbal or written communication to this effect. Withdrawal from the study will not impact access to care. The Principal Investigator may withdraw subjects for reasons related to safety or for administrative reasons. It will be documented whether or not each subject completes the study. Subjects who do not complete the intervention will continue to be contacted to complete follow-up visits (Month 1 and 6) to collect final evaluations and assess adverse events.

## 5 Statistical Plan

## 5.1 Data Quality

Trained staff will review all forms prior to the completion of the study visit in an effort to minimize problems associated with missing values and incorrect skip patterns. All assessments will be recorded on final version of the electronic Case Reporting Forms (eCRFs). eCRFs will also be developed to capture the results of all biological assessments. All eCRFs will be completed using only participant identifying numbers and will not include names, addresses, or other data that could possibly be used to disclose the identity of the participant. Research staff will be responsible for entering all data into the secure web-based developed on REDCap (Research Electronic Data Capture). REDCap is designed to comply with HIPAA regulations. Data will be input with secure web authentication, data logging, and Secure Sockets Layer (SSL) encryption. REDCap allows multisite access. It allows real-time data entry validation (e.g. for data types and range checks), audit trails, and the ability to set up a calendar to schedule and track critical study events such as participant visits.

The data quality control process associated with data processing will consist of the following stages: potential subject pre-screening for eligibility, registration, subject eligibility confirmation, first data entry, second data entry in the form of 100% interactive verification, data validation, and data auditing. A random 5% of the questionnaires in each wave of data collection (i.e., baseline, 1- and 6-month) will be subjected to database auditing throughout the trial. This data quality control process ensures that all stages of the data handling process will be subjected to data quality control.

# 5.2 Sample Size and Power Determination

Our power analysis has been based on this primary aim. Our primary hypothesis is that participants who received rapid induction will more likely be engaged in ongoing treatment at 1- and 6-month follow-up than participants who sought treatment at BAC/CRC. We will test this hypothesis at a 5% level of significance. Our principal interest is in the comparison of engagement rates between the mobile intervention and BAC/CRC groups, at months 1 and 6. Preliminary data suggest an engagement rate of about 20-30% in the BAC/CRC group. Assuming a steady loss to attrition that yields 80% completers, and a within-subject correlation of 0.3, the methods of Diggle et al. (Diggle, Heagerty et al. 2002) show that our sample size of 125 in each group yields 80% power for differences of about 15% in engagement rates between the two groups (e.g., 80% power for BAC/CRC: 25% vs. Mobile: 40%, corresponding to a RR=1.6 and an OR=2.0)

**Propensity score model to account for non-randomized allocation:** The participants are not randomly assigned to the mobile rapid induction intervention and BAC/CRC groups, so it is possible that there will be confounding of the group effect with the effects of characteristics of the participants. We will use a propensity score approach (Rosenbaum 2002, Rothman, Greenland et al. 2008) to account for this. We will use a broad range of baseline variables as covariates in a logistic regression model predicting treatment group, including age, race/ethnicity, gender, number of previous overdoses, number of previous treatments for opiate use disorder, type of opioid used, and depression. The model will yield predicted probabilities of BAC/CRC group for all participants (the propensity score), and we will create a five-level ordinal variable based on the quintiles of the propensity score. We will then include this ordinal variable as a stratum variable in our models.

**Analyses for the primary aim:** i.e. to evaluate the impact of the mobile, transitional MAT intervention on its ability to engage participants in targeted, existing MAT treatment slots at 1- and 6-month post-enrollment. For each of the 1- and 6-month time points, we will classify participants as being engaged/not-engaged (where non-engaged will include dropped out or missing). We will compare the groups on engagement rates at the two time points using a repeated measures logistic regression model, incorporating the propensity score as described above (Diggle, Heagerty et al. 2002). The fixed effects will be binary indicators of treatment group and time point; we will test for a group by time interaction to assess whether the group effect differs at month 1 and month 6. As there are only two time points, we will use an unstructured covariance matrix to accommodate within-participant covariance.

**Analyses for Aim 2:** We will also use a repeated measures model to compare the groups on the ASI drug composite score at months 1 and 6. The model will be similar to that described for the engagement analyses of Aim 1, but with a beta distribution assumed for the response, to accommodate the bounded range (zero to one) of the ASI composite scores. We will compare the groups on the number of overdoses per patient using repeated measures Poisson regression models, if there is sufficient variability in the number of overdoses reported. If a low rate of overdoses causes convergence issues for the Poisson model, we will classify participants as having no overdoses versus at least one, and compare the groups using repeated measures logistic regression models.

**Missing data.** For the longitudinal analyses described above, premature discontinuation from treatment and occasional missing daily use indicators will lead to incomplete data. The repeated measures models described above can make use of all available data provided by subjects, but the inferences drawn from them will be unaffected by the missing data only if the missing data can be regarded as ignorable, essentially meaning that missingness can be predicted/explained from the baseline data and from responses obtained prior to drop-out. We will assess the sensitivity of our main analyses to the presence of missing data by performing a sensitivity analysis, in which we will obtain estimates of the group effect under various non-ignorability assumptions. We will use selection models to examine the effects of missing data (Robins, Rotnitzky et al. 1995), in which we will explicitly model the probability of premature discontinuation at a time point as a function of baseline characteristics and responses at previous time points, using logistic regression models, and incorporate the predicted probabilities into a weighted analysis of the main hypotheses.

Analyses for Aim 3: We will estimate the total costs and per-participant costs of rapid initiation of MAT for opioid treatment engagement and use a cost-offsets approach to determine the economic value of this novel strategy. A cost-offsets approach requires a comparison of the total cost of the intervention (proposed enhanced procedure or treatment as usual) to the future costs of healthcare utilization avoided (i.e., benefits) due to the intervention. Healthcare utilization and medical costs will be estimated before and after participants receive either rapid initiation of MAT for opioid treatment engagement or treatment as usual. Information on healthcare utilization will be collected from participants at each assessment when study-staff administer the Non-Medical and Other Services Form (NSMOS; detailed description in Instruments section). Medical costs associated with these treatments/services will be estimated using Medicaid data. Costs of the intervention will be collected by [name], using the Drug Abuse Treatment Cost Analysis Program (DATCAP; detailed description in instruments section). She will interview staff in order to collect information on economic resource and cost variables such as staff salaries and benefits, study supplies and materials, major equipment, contracted services. building and facilities, and miscellaneous resources and costs. Recognizing that full-time staff members may devote only part of their work time to the proposed study, she will conduct a time-in-motion study with relevant study staff in order to track their time devoted to this study. Adjustments will then be made to salaries and benefits to reflect appropriate compensation attributed to this study. Similar adjustments will be made to reflect the time that some equipment, buildings and facilities, and miscellaneous resources and costs are attributed to the proposed study.

Differences in pre-post medical costs will be used as an estimate of the value of downstream costs avoided due to the intervention. We will compare these differences across groups for statistical significance. We hypothesize that the medical costs after the intervention will be significantly lower for the participants that receive rapid initiation of MAT for opioid treatment than for the participants that receive treatment as usual. The economic value of this novel intervention will be positive if the costs of this novel intervention are outweighed by the medical cost savings that result from participants obtaining long-term and consistent opioid treatment. The proposed intervention is expected to aid with this process. Therefore, we hypothesize that the cost of rapid initiation of MAT for opioid treatment will be outweighed by the resulting avoidance of healthcare utilization costs.

We conduct our cost analyses from the perspective of the City of Philadelphia Department of Public Health since they may decide to scale-up the proposed services for other Philadelphia residents at risk of substance use overdose. Thus, we focus on healthcare utilization costs avoided as benefits of the proposed services. We may extend our analysis later to use a societal perspective that would consider other economic costs, such as criminal justice costs, unemployment costs, and participant costs (e.g., travel, work time missed, childcare expenses, etc.). Inclusion of the economic costs avoided due to opioid use disorder treatment will make the economic value of the proposed intervention even more positive than it is hypothesized to be when considering only healthcare utilization costs avoided due to opioid use disorder treatment.

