# 1 Study Summary

Title	Rapid initiation of buprenorphine/naloxone to optimize MAT utilization in Philadelphia		
Short Title	Rapid initiation of BUP/NX		
Study overview	The proposed research will evaluate the ability of a mobile, rapid induction procedure to engage individuals in ongoing medication assisted treatment. A total of 250 untreated ndividuals meeting criteria for opioid use disorder and at high risk of opioid overdose will be enrolled in the study. Recruitment will take place in two targeted neighborhoods of Philadelphia (Kensington and South Philadelphia) with a high prevalence of fatal and non- fatal opioid overdose. A total of 250 participants will be engaged in the research. Following nformed consent and determination of eligibility, 125 individuals will be enrolled as they engage with the mobile, rapid induction team and 125 individuals will be enrolled as they seek treatment from the CRC Episcopal Hospital (serving Kensington area) or BAC/CRC Hall Mercer Community Mental Health (serving South Philadelphia). The intervention group will receive four weeks of treatment with buprenorphine /naloxone and support for treatment engagement provided by a case manager and a peer recovery specialist. All participants will be assessed at baseline and then 1- and 6-month following enrollment. The primary endpoint for the study is continued enrollment in medication-assisted treatment at 6 months post enrollment.		
Study Duration	The estimated duration of study is 36 months. Individual study subject participation will last 6 months.		
Study Center(s)	The University of Pennsylvania will serve as the primary project location, and all recruitment and data collection efforts will be executed by University of Pennsylvania staff members. A subcontract has been established with Prevention Point Philadelphia and Public Health Management Corporation.		

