	case manager and PRS will work with the participants to belo them become engaged					
	in existing medication assisted treatment programs					
	• The type of ongoing treatment will be determined on an individual basis and will					
	include options of methadone maintenance, buprenorphine/naloxone treatment, or					
	extended-release naltrexone (XR-NTX).					
	Comparison on engagement rates in ongoing opiate use disorder treatment at the					
	two time points (1- and 6-months) using a repeated measures logistic regression					
	model, incorporating the propensity score (to correct for non-randomized trial)					
	Evaluate the change in substance use and severity of addiction using a repeated					
	measures model to compare the groups on the ASI drug composite score at months					
	1 and 6.					
Statistical	Compare of the number of overdoses per participant between groups using repeated					
Mothodology	measures Poisson regression models, if there is sufficient variability in the number of					
wethodology	Poisson model, we will classify participants as baying no overdoses versus at least					
	one and compare the groups using repeated measures logistic regression models					
	
 
Evaluation of the sensitivity of our main analyses to the presence of missing data by
 
					
	performing a sensitivity analysis, in which we will obtain estimates of the group effect					
	under various non-ignorability assumptions, using selection models to examine the					
	effects of missing data, using logistic regression models, and incorporate the					
	predicted probabilities into a weighted analysis of the main hypotheses.					
	The study will be monitored by the PIs and co-investigators, and Philadelphia Department					
Data and Safat	of Public Health Institutional Review Board, as well as by regulatory committees at the					
Data and Salety	University of Pennsylvania (i.e., IRBs, OHR) and Center for Studies of Addiction Data Safety					
Monitoring Plan	Monitoring Board (Penn DSMB). During the course of the study, safety and data quality					
	monitoring will be performed on an ongoing basis by the Principal Investigator and the study					
	staff.					

The information that follows constitutes the research protocol for the Rapid initiation of buprenorphine/naloxone to

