# 3.2 Innovation

Rapid induction with buprenorphine/naloxone in the community is the core innovation of the proposed research. By reducing time and geographic barriers to treatment and the control of withdrawal symptoms, the intervention will provide a one-month opportunity to link participants to an appropriate, ongoing treatment provider. This use of MAT is an innovation designed to minimize common barriers to treatment engagement. The use of buprenorphine will also allow for the transition to other MAT strategies that may be more appropriate for the individual, including methadone maintenance treatment, buprenorphine treatment, or treatment with extended-release naltrexone. The ability to engage individuals with opioid use disorder in their home environment is another important innovation of the proposed research. The mobile engagement team will include a Nurse Practitioner, a Case manager, and a Certified Peer Recovery Specialist and will begin inductions on the mobile medical unit or in the individual's home. The mobility of the team is an innovation allowing easy access to individuals who indicate interest in treating their opioid use disorder. We will assess treatment status at six months post enrollment as our primary outcome measure. With the permission of the participant, the CARES Integrated Data Systems Service Utilization database will be available to identify involvement with drug treatment and other services provided by the City prior to and following the enrollment in the study.

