#### 3.4 Study Objectives

The proposed research will evaluate the ability of a mobile, rapid induction procedure to engage individuals in ongoing medication assisted treatment. Individuals meeting criteria for opioid use disorder and at high risk of opioid overdose will be enrolled in the study. Recruitment will take place in two targeted neighborhoods with a high prevalence of fatal and non-fatal opioid overdose. A total of 250 participants will be engaged in the research at the time they seek treatment. Following informed consent and determination of eligibility, 125 individuals will be enrolled as they engage with the mobile, rapid induction team and 125 individuals will be enrolled as they seek treatment from the BAC/CRC. All participants will be assessed at 1- and 6-month following enrollment. These assessments will provide data able to address each of the three aims.

- **Aim 1:** To evaluate the impact of the mobile, transitional MAT intervention on its ability to engage participants in targeted, existing MAT treatment slots at 1- and 6-month post-enrollment.
- Aim 2: To evaluate the impact of the mobile intervention on subsequent drug use and overdoses at 6-month postenrollment.
- Aim 3: To assess the acceptability and costs of the intervention. We will document the program and patient costs of delivering and participating in the intervention.

Assessments will also provide data on factors that are considered to be important determinants of retention in treatment—duration of opioid use; prior number of treatment attempts; frequency of recent use; and, depression. In addition to age, gender, and race these variables will be used in the proposed propensity analyses.

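### The summary names month-6 treatment status as the primary endpoint, but the stated 80% power belongs to the effect averaged over months 1 and 6; month-6 power is about 62% to 72%

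*Combined protocol and SAP*

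**What the plan says.** Two places make month 6 primary. The study overview in section 1 states: "The primary endpoint for the study is continued enrollment in medication-assisted treatment at 6 months post enrollment". Section 3.2 states: "We will assess treatment status at six months post enrollment as our primary outcome measure".

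Everything that drives the analysis covers both visits:

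- Aim 1 (sections 1 and 3.4) is to "engage participants in targeted, existing MAT treatment slots at 1- and 6-month post-enrollment".
- The Statistical Methodology row of section 1 compares engagement at the "two time points (1- and 6-months) using a repeated measures logistic regression" model.
- In section 5.2 the primary hypothesis refers to both follow-ups, and the text adds: "Our principal interest is in the comparison of engagement rates between the mobile intervention and BAC/CRC groups, at months 1 and 6".
- The paragraph on analyses for the primary aim fits one repeated-measures logistic model to both visits, with group and time as fixed effects and a test of group by time. Dropped-out and missing participants count as not engaged. It does not say which contrast is primary, or what may be concluded about month 6 from the model.

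Section 3.8.1, the endpoint section, names treatment engagement without a time point. Section 3.7 says that ongoing engagement is the endpoint on which the study is powered, also without a time point.

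On power, section 5.2 says "We will test this hypothesis at a 5% level of significance" and then "Assuming a steady loss to attrition that yields 80% completers", with a correlation of 0.3. From these it concludes that "our sample size of 125 in each group yields 80% power for differences of about 15% in engagement rates between the two groups". It gives 25% versus 40% as the example for 80% power and a comparison-group rate of about 20% to 30%.

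**The concern.** The endpoint that the summary announces is not the quantity that the study is powered on or that the primary analysis most naturally estimates. A within-subject correlation plays no part in a single-visit comparison, so the 80% was not computed for month 6. Anyone who reads it next to the summary's endpoint will take month 6 to be better powered than it is.

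The two quantities can also give different answers. Month 1 falls at the end of the study-supplied month of medication and linkage support (sections 3.1 and 4.9.1), so unequal effects at the two visits are plausible. An averaged effect could be significant mainly because of month 1, and be reported against an endpoint defined at month 6. The comparison is open-label and non-randomized, so the deciding contrast should be fixed before results are seen.

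**Working it through.** **Inputs.** From section 5.2: 125 per group, 80% completers (100 per group), rates 25% and 40%, correlation 0.3, 5% level. The sides of the test are not stated; two-sided is assumed. From section 3.7: anticipated follow-up of 95% at month 1 and 90% at month 6. From the primary analysis: missing counts as not engaged.

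**Formula.** Two proportions, pooled variance under the null, d = 0.15:

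power = Φ{[d√n − 1.960·√(2p̄(1−p̄))] / √(p₁q₁ + p₂q₂)}

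With p̄ = 0.325, √(2 × 0.325 × 0.675) = 0.6624 and √(0.1875 + 0.2400) = 0.6538.

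**Step 1: reproduce the plan's figure.**
- Single visit, 80% power: n = (1.960 × 0.6624 + 0.842 × 0.6538)² / 0.15² = 152 per group.
- Two visits averaged: multiply by (1 + 0.3)/2 = 0.65, giving about 99 completers. 99/0.8 = 124, against 125 stated.
- Power with 100 completers: effective n = 100/0.65 = 153.8, so Φ[(1.8605 − 1.2983)/0.6538] = Φ(0.860) = 80.5%.
- A one-sided test would give 88%, so two-sided is the likelier intent.

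**Step 2: month 6 alone, 25% versus 40%, two-sided 5%.**
- n = 100: Φ[(1.5000 − 1.2983)/0.6538] = Φ(0.309) = 62%.
- n = 125: Φ[(1.6771 − 1.2983)/0.6538] = Φ(0.579) = 72%.
- Difference detectable with 80% power from a 25% comparison rate: 18.7 points at 100 per group, 16.6 at 125.
- Comparison rate 20% to 30% with a 15-point difference: 66% to 59% at 100 per group; 76% to 69% at 125.

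**Step 3: if 25% and 40% are rates among those followed.** Assume equal follow-up in both groups, every missed visit scored as not engaged, and no recovery of status from records, with 125 per group.
- 90% follow-up: 22.5% versus 36%, power 65%.
- 80% follow-up: 20% versus 32%, power 58%.

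These can move either way. If provider or city records settled half of the missed visits, they become 69% and 65%. If overall follow-up of 90% split as 93% usual care and 87% mobile (an assumed illustration), the rates become 0.25 × 0.93 = 23.25% and 0.40 × 0.87 = 34.8%, and power is about 52%.

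**Step 4: propensity strata.** No figure above deducts for adjusting for quintiles, and the documents give none to use. As an assumed illustration, a 10% loss of information takes the two-visit power from 80.5% to about 76% (n = 138.5) and month 6 at 125 per group from 72% to about 67% (n = 112.5).

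**Step 5: an effect at month 1 only (assumed rates).** Take 25% versus 40% at month 1, 25% in both groups at month 6, 125 per group and correlation 0.3.
- Hand check: the averaged difference is 7.5 points. Its variance is [0.4875 + 0.5548]/(4 × 125) = 0.002085, standard error 0.0457. Φ(0.075/0.0457 − 1.96) = Φ(−0.32), about 38%.
- Simulation of the repeated-measures logistic model (40,000 replicates, no propensity strata): averaged effect significant in favour of mobile in 39%; significant with no significant interaction in 18%; month-6 contrast favours mobile in 2.6%, the nominal rate.
- A second simulation by a different method gave 38% and 18%.

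**The case against.** The best defence is that the operative parts agree with one another. Aim 1, the hypothesis, the power calculation and the primary analysis all use both visits; section 5.2 ties its power to the primary aim; and the 80% reproduces. On this view the outliers are one summary sentence and one sentence in the Innovation narrative, and the shortfall exists only if those sentences prevail. Much of this stands. The planned analysis is not obscure, and under the two-visit reading the stated power is correct. But the two sentences are the only places that give the primary endpoint a time point, and the endpoint section does not settle it. At least one side has to change.

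It is also fair to say that the month-1-only rates are hypothetical, that the plan states what its interaction test is for, and that visit-specific reporting after a significant interaction is customary. The custom does not cover the 18% of trials in Step 5 where the averaged test succeeds and no interaction is flagged.

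Some stronger readings are tempting, but the documents do not support them:

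- A reader might infer that the sample size or the 80% is miscalculated. Step 1 shows that it is not.
- A reader might see a contradiction between 80% completers and the 90% follow-up expected at month 6. A planning rate more conservative than the expected rate is a margin, not an error, although the text does not say so.
- A reader might treat the unstated sidedness as a way out, since one-sided month-6 power at 125 per group is 81.6%. One-sided testing would make the plan's own calculation 88%, and with its 80% completers month 6 would have 73.5%. The omission is missing detail.
- A reader might take the 65% and 58% as lower bounds. Unequal follow-up or propensity adjustment could put power below them.

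**Conclusion.** The inconsistency is real and should be fixed. The 80% power is correct for the effect averaged over months 1 and 6, but it does not describe the month-6 endpoint named in sections 1 and 3.2. For 25% versus 40% at two-sided 5%, month-6 power runs from about 62%, if the plan's 80% completers are the analysed number, to about 72%, if all 125 per group are analysed at those rates. The detectable difference is about 17 to 19 points rather than 15. Power is lower than 72% if the rates apply only to those followed and missed visits count as not engaged. All of these figures precede any loss from propensity adjustment.

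The finding does not show that the trial is too small for its two-visit hypothesis. The month-1-only results show how the two quantities can part company under assumed rates; they are not a forecast.

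**What to change.** Name one primary contrast and state it in the same words in sections 1, 3.2, 3.8.1 and 5.2 and in the primary analysis. Either choice is defensible.

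- **(a) Month 6 is primary.** The month-6 group contrast, taken from the planned repeated-measures model with group, time, group by time and propensity stratum, is the single primary test at two-sided 5%. Month 1 and the averaged effect become secondary. Section 5.2 restates month-6 power as about 62% to 72% for 25% versus 40%, before propensity adjustment. Cost: the stated power is less favourable. Keeping 80% at a 15-point difference would need 152 evaluable per group.
- **(b) The average over months 1 and 6 is primary.** The 80% stands, described as before propensity adjustment. The sentences in sections 1 and 3.2 are changed to match. The month-6 contrast is always reported, and any claim about month 6 rests on that contrast alone, whether or not the interaction is significant. Cost: month 6 no longer decides the study.

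Under either option, a few added phrases would close the remaining gaps: the sides of the test, whether 25% and 40% refer to all enrolled or to those followed, whether provider or city records can settle status after a missed visit, and that the 80% completer rate is a planning margin if that is what it is. These are wording changes, with no extra participants or data collection.
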